7.2.2.7. Change in Physical Activity Measures as Assessed by a Biosensor

No statistical analysis is planned for this endpoint, but summary statistics will be produced for the following variables:

- Daily Step Count
- Daily Average Metabolic Equivalent of Tasks (METs)
- Daily Sleep Duration

7.3. Supplementary Information for Efficacy Tables, Listings and Figures

An overall forest plot will be produced showing the adjusted treatment differences/ratios and 95% confidence intervals for the primary and secondary efficacy endpoints. This will be produced for the ITT population and repeated for the ITT (15 Years or Older) population.

8. SAFETY ANALYSES

8.1. Safety Analyses

8.1.1. Overview of Planned Safety Analyses

The safety analyses will be based on the ITT population, unless otherwise specified.

[Table 5](#) provides an overview of the planned analyses, with further details of data displays being presented in [Appendix 13: List of Data Displays](#).

Table 5 Overview of Planned Safety Analyses

Display Type	Data Displays Generated		
	Table	Figure	Listing
Adverse Events			
Overview	Y		
AEs for Subjects not in ITT			Y ^[2]
Pre-Treatment AEs			Y
On-Treatment AEs	Y ^[3]		Y
Post-Treatment AEs	Y		Y
Most Frequent On-Treatment AEs (≥3% after rounding)	Y		
Top Ten Most Common On-Treatment AEs	Y		
Drug-Related AEs	Y		
Drug-Related SAEs	Y		
AEs Leading to Withdrawal	Y		Y
On-Treatment SAEs	Y		Y
Post-Treatment SAEs	Y		Y
Common On-Treatment Non-Serious AEs (≥3% without rounding including event numbers and drug-related event numbers)	Y		
On-Treatment SAEs (including event numbers and drug-related event numbers)	Y		
On-Treatment Fatal AEs (including event numbers and drug-related event numbers)	Y		
Post-Treatment Fatal SAEs (including event numbers and drug-related event numbers)	Y		
AEs of Special Interest	Y ^[1]		
SAEs of Special Interest	Y		
Relationship of AE System Organ Class, Preferred Term and Verbatim Text	Y		
Record of all Preferred Term's That Could Have Mapped to Special Interest Terms	Y		
Pneumonia			
On-Treatment Pneumonia	Y		Y
Post-Treatment Pneumonia	Y		Y
Chest X-ray			Y
Severe Asthma Exacerbations			
Severe Asthma Exacerbations	Y ^[3]		Y

Display Type	Data Displays Generated		
	Table	Figure	Listing
Other			
Vital Signs	Y		Y
Change from Baseline in Vital Signs	Y		
Family History of CV Risk Factors	Y		Y
IP Inhaler Malfunctions			Y

NOTES :

- Y = Yes display generated.
- [1]: Display will be based on the ITT population and repeated for the ITT (12-17 Years Old) population
- [2]: Display will be based on the inverse of the ITT population i.e. all subjects not in the ITT population
- [3]: Display will be based on the ITT population and repeated for the ITT (12-17 Years Old) population and also for the ITT (15 Years or Older) population

8.2. Supplementary Information for Safety Tables and Listings

8.2.1. Adverse Events

The version of MedDRA used to report the study will be noted in a footnote of the AE overview table.

For the main on-treatment and post-treatment AE tables, the number and percentage of subjects with all adverse events (regardless of causality) will be summarized for each treatment by system organ class (SOC) and preferred term (PT). The ordering of the SOCs and the PTs within the SOCs will both be in descending order of total incidence. A SOC will not be presented when the overall incidence for any adverse event within the particular system is 0. If the total incidence for any two or more adverse events is equal, the events will be presented in alphabetical order.

8.2.1.1. Adverse Events of Special Interest

The number and percentage of subjects with adverse events of special interest to FF and/or VI will be summarized for each treatment by special interest term, subgroup and preferred term (PT). The ordering of the special interest terms, the subgroups and the PTs within them will all be in descending order of total incidence. If the total incidence for any two or more adverse events is equal, the events will be presented in alphabetical order. This summary will include both on-treatment and post-treatment AEs.

10.1. Appendix 1: Definitions for Per Protocol Population

10.1.1. Protocol Deviations Impacting the Per Protocol Population

A protocol deviation which could affect all treatment periods will be considered a full deviation and will result in exclusion from the Per Protocol population. A protocol deviation which would only affect a specific treatment period will be considered a partial deviation and the data from the treatment period affected by the deviation will be excluded. If a subject has partial deviations in both treatment periods then the subject will be excluded from the Per Protocol population, however if a subject only has partial deviations in 1 treatment period, they will be considered part of the PP population but their data from the treatment period affected by the deviations will be excluded.

Reasons for protocol deviations that will impact the Per Protocol population include the following:

Number	Exclusion Description	Full or Partial?
1	Failure of inclusion criteria 3, 4, 5, 6 or 9; exclusion criteria 1, 3, 4, 7, 8, 9, 12, 13 or 15; randomization inclusion criteria 1 or 2 or randomization exclusion criteria 2, 4 or 5 as described in Section 6 of the protocol [GlaxoSmithKline Document Number 2015N231308_03].	Full
2	Remaining in the study after meeting the following withdrawal criteria described in Section 6 of the protocol [GlaxoSmithKline Document Number 2015N231308_03]: 
 Severe asthma exacerbation 	Full if during 1 st treatment period. Otherwise partial.
3	Taking of prohibited medication as described in Section 7.10.2 of the protocol [GlaxoSmithKline Document Number 2015N231308_03], where that medication could conceivably have an effect on a subject's efficacy.	Full if it affects both periods. Otherwise partial.
4	Overall treatment compliance for either DISKUS or ELLIPTA of < 80% or > 120%. (The protocol required subjects to take their study medication each day. For reporting and analysis purposes, treatment compliance of 80% and 120% are defined here as lower and upper limits for subjects to remain in the Per Protocol population.) Only treatment periods affected will be excluded.	Partial
5	Taking the wrong treatment at any time during the study. Only treatment periods affected will be excluded.	Partial
6	The 12 hour exercise challenge on day 14 of a treatment period (Visit 4/7) occurring on day 11 or earlier of the treatment period i.e. 11 days or less after day 0 of the treatment period (Visit 2/5).	Partial
7	The pre-exercise FEV ₁ prior to the 12 hour challenge on day 14 of a treatment period (Visit 4/7) occurring <11 hours or >13 hours after the previous dose of study medication.	Partial

Apart from any incorrect treatment deviations, all full and partial protocol deviations will be agreed upon prior to unblinding the study.

In addition to the subject level protocol deviations mentioned above, a given FEV₁ measurement must not be within 6 hours after the last use of rescue medication to be included in the Per Protocol analysis of the primary endpoint. Any FEV₁ measurement that was taken within 6 hours after the last use of rescue medication will be considered missing in the Per Protocol analysis of the primary endpoint.

Any FEV₁ measurements that are labelled as 'Unacceptable' will be considered missing for both the Intent-to-Treat and the Per Protocol populations.

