7.10. Concomitant Medications and Non-Drug Therapies

The names, doses, and regimens of the asthma medications taken during the 12 weeks prior to Visit 1 must be recorded in the Concomitant Medications section in the eCRF.

All concomitant medications taken during the study will be recorded in the eCRF. The minimum requirement is for the reporting of the drug name and dates of administration. Study provided albuterol/salbutamol should NOT be recorded in the eCRF.

Asthma medications taken after the final clinic visit will not be recorded in the eCRF.

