8.3. Efficacy

8.3.1. Spirometry

Subjects should abstain from drinking beverages with high caffeine content such as tea or coffee for 4 hours prior to the spirometry procedure.

FEV₁ should be measured using spirometry equipment that meets or exceeds the minimal recommendations of the American Thoracic Society (ATS)/European Respiratory Society (ERS) [[Miller](#), 2005]. All sites will use standardized spirometry equipment provided by an external vendor. Full FEV₁ and FVC will be conducted at Visit 1, and pre-dose at Visit 5, and prior to each exercise challenge at Visits 2, 3, 4, 6 and 7.

For full FEV₁ and FVC testing at Screening and at randomisation (Visit 2), at least two valid and two repeatable (with no more than 8) efforts should be obtained using ATS/ERS guidelines. For all other visits where full FEV₁ and FVC testing is performed (prior to each exercise test at visits 3, 4, 6 and 7), at least two valid efforts should be

obtained. At each time point, the largest FEV₁ and FVC should be recorded, even if they do not come from the same effort.

Serial FEV₁ measurements only (not FVC) will be conducted serially as described in Time and Events Table [Table 3](#) following each exercise challenge at Visits 2, 3, 4, 6 and 7.

Subjects must have a FEV₁ of at least 70% of their predicted normal value to be eligible to take part in the study at Visit 1.

After Visit 1, subjects will always be required to withhold their albuterol/salbutamol for at least 6 hours before each clinic visit.

Subjects must not administer study drug prior to coming to the clinic on study visit days.

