8.3.1.1. Target FEV₁ Calculations

Three target FEV₁ values will be calculated from the pre-exercise FEV₁ to determine subject eligibility and for monitoring the safety of the subject prior to exercise challenge testing:

1. The FEV₁ value that represents a $\geq 20\%$ decrease in FEV₁, which is the eligibility criterion.
2. The FEV₁ value that represents a $\geq 40\%$ decrease in FEV₁, which will serve as an alert for severe bronchoconstriction and need for administering rescue treatment.
3. The FEV₁ value that represents a $\geq 95\%$ recovery of the FEV₁ result.

Subjects should be monitored until they reach a recovery level where their FEV₁ value represents a 95% recovery of the pre-exercise FEV₁ result. Additional spirometry and rescue medication may be used as needed (See Section [8.3.2.1](#)).

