8.3.2.1. Worsening of Asthma during Exercise Challenge

Exercise challenges may be stopped at any time during the assessment for worsening asthma. Guidelines for treatment are provided in the SRM.

If a subject's FEV₁ decreases to $\geq 40\%$ from their pre-exercise FEV₁ following exercise challenge, he/she must receive rescue therapy. If he/she requires rescue therapy with anything other than MDI or nebulized albuterol/salbutamol or ipratropium (secondarily) following the exercise challenge assessment, he/she is not allowed to continue in the study (see Section 6.4.1).

The subject should not leave the clinic until FEV₁ returns to within 95% of the baseline FEV₁ target recovery value or the subject is judged medically stable by the investigator to leave the clinic.

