Primary Analysis Populations	
 The ITT Population will comprise all subjects randomized to treatment and who received at least one dose of trial medication. Randomized subjects will be assumed to have received trial medication unless definitive evidence to the contrary exists. This will constitute the primary population for all analyses of efficacy measures and safety measures. Outcomes will be reported according to the randomized treatment allocation. The PP Population will consist of all subjects in the ITT Population who do not have any full protocol deviations and have at least one treatment period without a partial deviation. Protocol deviations can either be full or partial. Subjects with only partial deviations in 1 treatment period will be considered part of the PP population but their data from the treatment period affected by the deviations will be excluded. The decision to exclude a subject, or part of their data, from the PP Population will be made prior to breaking the blind. This population will be used for confirmatory analyses of the primary efficacy endpoint only.

Overview	Key Elements of the RAP
Hypothesis	
Demonstration of efficacy will be based on a hypothesis testing approach, whereby the null hypothesis is that there is no difference between treatment groups for the endpoint of interest and the alternative hypothesis is that there is a difference between treatment groups
Primary Analyses	
The primary efficacy endpoint will be analysed using a mixed model repeated measures (MMRM) model allowing for fixed covariate effects of treatment, period baseline FEV₁, the mean of the two period baseline FEV₁ values, sex, age, treatment period and smoking history (number of pack years) as fixed effects, and a random intercept for each subject. The covariate-adjusted means for the primary endpoint for each treatment group will be presented together with the estimated difference between the treatment groups, a 95% confidence interval and a 2-sided p-value allowing the null hypothesis to be tested.

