7. EFFICACY ANALYSES

7.1. Primary Efficacy Analyses

7.1.1. Overview of Planned Primary Efficacy Analyses

The primary efficacy endpoint is the maximal percent decrease from pre-exercise FEV₁ following exercise challenge at 12 hours post evening dose at the end of the 2-week treatment period.

Table 3 provides an overview of the planned efficacy analyses, with full details of data displays being presented in [Appendix 13: List of Data Displays](#).

Table 3 Overview of Planned Primary Efficacy Analyses

	Stats Analysis		Summary		Individual
	T	F	T	F	L
Primary Analysis					
Max % Decrease - ITT	Y	Y	Y		
Sensitivity Analysis					
Max % Decrease - PP	Y	Y	Y		
Max % Decrease - ITT (15 Years or Older)	Y	Y			
Supporting Analyses and Other Summaries					
Max % Decrease - ITT (12-17 Years Old)			Y		
Max (L) Decrease - ITT	Y	Y	Y		
Max (L) Decrease - ITT (15 Years or Older)	Y	Y			

NOTES :

- T = Table, F = Figure, L = Listing, Y = Yes display generated.
- Stats Analysis = Represents TFL related to any formal statistical analyses (i.e. modelling) conducted.
- Summary = Represents TFL related to any summaries (i.e. descriptive statistics) of the observed raw data.
- Individual = Represents FL related to any displays of individual subject observed raw data.

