10.6.3. Efficacy

Primary Endpoint

Maximal % Decrease from Pre-Exercise FEV₁ Following 12 Hour Challenge at Day 14

The primary endpoint will be derived as follows:

$$\frac{\text{Pre-Exercise FEV}_1 - \text{Minimum Post Exercise FEV}_1}{\text{Pre-Exercise FEV}_1} \times 100$$

Where pre-exercise FEV₁ will be defined as the FEV₁ value collected immediately prior to the exercise challenge.

And the minimum post exercise FEV₁ will be the smallest FEV₁ value recorded from the planned post-challenge time points (5, 10, 15, 30, 45 and 60 minutes) using only those with an actual time that is no more than 65 minutes after the challenge stop time.

The minimum post exercise FEV₁ will only be calculated if there are at least the following non-missing FEV₁ values:

- A post-exercise measurement with an actual time of ≤ 17 minutes
- A post-exercise measurement with an actual time of ≥ 25 and ≤ 50 minutes

If there are not values meeting both of these criteria available then the endpoint will not be calculated and will be treated as missing.

Secondary and Other Endpoints

Maximal % Decrease from Pre-Exercise FEV₁ Following Exercise Challenge

Maximal percent decrease from pre-exercise FEV₁ will be derived for other time points in the same way as for the primary endpoint.

Maximal Decrease from Pre-Exercise FEV₁ (L) Following Exercise Challenge

Maximal decrease from pre-exercise FEV₁ (L) will be derived as:

$$\text{Pre-Exercise FEV}_1 - \text{Minimum Post Exercise FEV}_1$$

Where pre-exercise FEV₁ and minimum post-exercise FEV₁ are defined in the same way as for the primary endpoint and the same minimum number of non-missing FEV₁ values are required for the endpoint to be calculated.

Maximal % Decrease from Period Baseline FEV₁ Following Exercise Challenge

Maximal percent decrease from period baseline FEV₁ will be derived as:

$$\frac{\text{Period Baseline FEV}_1 - \text{Minimum Post Exercise FEV}_1}{\text{Period Baseline FEV}_1} \times 100$$

Where minimum post-exercise FEV₁ is defined in the same way as for the primary endpoint and the same minimum number of non-missing FEV₁ values are required for the endpoint to be calculated.

Secondary and Other Endpoints
Maximal Decrease from Period Baseline FEV₁ (L) Following Exercise Challenge
Maximal decrease from period baseline FEV ₁ (L) will be derived as:
Period Baseline FEV₁ – Minimum Post Exercise FEV₁

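### In the Per Protocol analysis of the primary endpoint, the 6-hour rescue rule can discard a deep fall already measured, because it also covers rescue given for that same challenge

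*SAP*

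**What the plan says.** **The PP rule.** SAP 10.1.1 states that, for the primary endpoint, an FEV₁ "measurement that was taken within 6 hours after the last use of rescue medication will be considered missing in the Per Protocol analysis". It applies reading by reading and does not distinguish rescue before the challenge from rescue after it.

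**The completeness rule.** SAP 10.6.3, repeated in 10.7.2, calculates the post-exercise minimum only if there is one reading at 17 minutes or earlier and another between 25 and 50 minutes. The consequence of falling short is stated: "If there are not values meeting both of these criteria available then the endpoint will not be calculated and will be treated as missing".

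**Rescue at the challenge.** Under Protocol 8.3.2.1 (and 6.4.1), a subject whose FEV₁ falls by 40% or more after exercise "he/she must receive rescue therapy". For recovery generally, Protocol 8.3.1.1 says "Additional spirometry and rescue medication may be used as needed".

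**Rescue before the challenge.** Protocol 8.3.1: "After Visit 1, subjects will always be required to withhold their albuterol/salbutamol for at least 6 hours before each clinic visit".

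**Role of the PP population.** SAP section 1: "This population will be used for confirmatory analyses of the primary efficacy endpoint only". SAP 7.1.1 lists "Max % Decrease - PP" under sensitivity analysis.

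**Recording of rescue.** Protocol 7.10: "Study provided albuterol/salbutamol should NOT be recorded in the eCRF". Protocol 7.1 has rescue use noted once a day in a paper diary.

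**The concern.** The 6 hours match the withholding requirement, which protects the pre-exercise reading from a recent bronchodilator. As drafted, the rule also reaches rescue given because the challenge provoked bronchoconstriction. That rescue complies with the protocol, and the fall that triggers it is the outcome being measured.

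Whether a PP value survives can therefore depend on how large the fall was. The random-intercept model does not repair missingness that depends on the lost value. If FF/VI protects better than FP, more FP values are lost, the FP mean is pulled down, and the PP difference moves toward zero. The analysis meant to confirm the primary result could then disagree with ITT because of this rule alone.

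**Working it through.** **1. The plan's own figure.** Protocol 10.2.1–10.2.2 gives 90.1% power with 56 evaluable subjects, a true difference of 5 and within-subject SD 8. For a 2×2 crossover, SE = 8 × √(2/56) = 1.512 and the noncentrality is 5/1.512 = 3.307. On 54 df at two-sided 5% the power is 90.11%, so the figure is reproduced and 56, 5 and 8 can be used below.

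**2. The rules applied in order.** Planned readings are at 5, 10, 15, 30, 45 and 60 minutes, so every reading after challenge rescue falls inside the 6-hour window.

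| Rescue given just after | Readings kept in PP | Reading at ≤17 min | Reading at 25–50 min | PP value |
|---|---|---|---|---|
| 5 min | 5 | yes | no | missing |
| 10 min | 5, 10 | yes | no | missing |
| 15 min | 5, 10, 15 | yes | no | missing |
| 30 min | 5, 10, 15, 30 | yes | yes | kept |

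The reading that shows the deep fall is not itself blanked. The later ones are, and the completeness rule then voids the period. The subject's other period stays in the model. ITT has no rescue rule and keeps the value.

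**3. How many values could be lost.** Not in the documents, so assumed: normally distributed falls, between-subject SD 8 to 12, FP mean fall 15% to 30%, and every fall of 40% or more rescued before 25 minutes. The chance that an FP value reaches 40 is 1 − Φ((40 − mean)/√(SD_between² + 8²)). Example: mean 25 and SD_between 8 give z = 15/11.31 = 1.326 and probability 0.092; times 56, that is 5.2 values.

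**4. Effect on the estimate.** 2,000 simulated trials per scenario, 56 subjects, two sequences 1:1, REML random-intercept model with treatment and period (baseline covariates omitted). Without deletion the mean estimate was 4.95–5.04; the Monte Carlo SE is about 0.035. Each cell gives between-subject SD 8 / 12.

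| FP mean fall | FP values lost, all rescued early | FF/VI values lost | PP estimate, all rescued early | PP estimate, half rescued early |
|---|---|---|---|---|
| 15% | 0.7 / 2.4 | 0.2 / 1.1 | 4.76 / 4.66 | 4.92 / 4.86 |
| 20% | 2.2 / 4.6 | 0.8 / 2.3 | 4.53 / 4.40 | 4.75 / 4.74 |
| 25% | 5.2 / 8.4 | 2.2 / 4.6 | 4.16 / 4.04 | 4.61 / 4.65 |
| 30% | 10.6 / 13.6 | 5.2 / 8.3 | 3.52 / 3.62 | 4.43 / 4.56 |

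A separate large-sample calculation with known variance components (between-subject SD 8–10, FP mean 15–25%) gives 4.1–4.8 with full deletion. If falls of 30% or more were also rescued early, as the as-needed provision would allow, it gives 3.2–4.2.

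**5. Disagreement with ITT.** Share of simulated trials with ITT p<0.05 but PP p≥0.05, between-subject SD 8 / 12:

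| FP mean fall | All rescued early | Half rescued early |
|---|---|---|
| 15% | 2.8% / 5.8% | 1.9% / 3.3% |
| 20% | 6.7% / 10.4% | 3.4% / 5.8% |
| 25% | 14.8% / 19.8% | 7.1% / 9.4% |
| 30% | 27.8% / 32.2% | 10.6% / 11.7% |

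Without the rule these shares are zero by construction, because no other PP exclusion was simulated.

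**The case against.** **Scope.** Only the PP analysis of the 12-hour endpoint is touched. ITT is primary, PP is a sensitivity analysis, and it lies outside the hierarchy in SAP 10.10.1. This stands and limits the weight of the point.

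**Size.** The FP mean fall, between-subject SD and frequency and timing of rescue are all assumed, and treatment guidance for the challenge sits in the Study Reference Manual, which is not available here. No passage supports a 30% mean fall after weeks of FP; a 20% fall at one time point is only the entry threshold. This stands for the size, not for the mechanism. The 15–25% rows deserve more attention than the last.

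**The zero benchmark.** SAP 10.1.1 lists seven other PP deviations. If 10% of period values were lost at random (an assumption), 6–10% of trials would already show ITT significant and PP not. The increment from the rescue rule stays similar, so the effect remains.

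**Unrecorded rescue times.** If clinic rescue has no recorded time, the rule cannot be run as written and the predicted loss may not occur. That is right: the figures assume the times are available. The missing data source is a separate gap and adds nothing to the bias argument.

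**Excluding post-rescue readings is a legitimate PP aim.** It is, but here it removes a fall measured before any rescue was given.

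**Conclusion.** The concern holds. Read together, SAP 10.1.1 and 10.6.3 void a PP value whose deep fall was measured before rescue, whenever that rescue precedes the first reading at 25 minutes or later. No other passage prevents this. The mechanism follows from the text and needs no assumptions.

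The size does need them, and it runs from negligible (a loss of about 0.1 on a true difference of 5, with an FP mean fall of 15% and half of the deep falls rescued early) to material (about 1.5, at 30% with all rescued early). The direction, toward no difference, follows if FP has the deeper falls. No error rate changes. What is at risk is the reading of the PP analysis as confirmation of the primary result, so the text should be corrected although the primary test does not depend on it.

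**What to change.** Edit SAP 10.1.1 only, before unblinding:

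- Limit the 6-hour exclusion to rescue taken before the pre-exercise FEV₁ of the 12-hour challenge.
- Add: *FEV₁ measurements taken after rescue given during or after that challenge are kept, and the minimum post-exercise FEV₁ is derived as in Section 10.6.3.*
- Name the data source for the time of last rescue before the challenge.

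Sections 10.6.3 and 10.7.2 stay as they are, so ITT and PP share one derivation. The cost is one or two sentences and a named source, with no change to the ITT derivation or study conduct.

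The downside is that a PP value may include post-rescue readings. Where rescue precedes the true nadir the fall may be understated, possibly more often on FP, exactly as in ITT. A narrower alternative is to use the pre-rescue minimum when rescue was given for that challenge. It would require waiving the 25–50 minute requirement for PP, so the two derivations would differ. It would not reduce the understatement either, since the minimum over all readings can never exceed the minimum over the pre-rescue ones.
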